#### 3.4 Primary outcome measures

The primary objective will be measured using GAD-7 scores, which is a participant-reported screening tool and severity measure for generalised anxiety disorder (GAD).

- The outcome measure for **reliable improvement of GAD** is defined as participants who reach a score reduction of 5 or more from baseline to week 24. Such a reduction amounts to a clinically important change. Some reliable improvement is defined as participants who reach a score reduction of 1 – 4 from baseline to week 24. No reliable improvement is defined as participants who reach no score reduction from baseline to week 24.
- The outcome measure for **clinically significant improvement of GAD** is defined as participants with a score of 10 or more at baseline, who reach 9 or fewer by week 24.
- The outcome measure for **recovery of GAD** is defined as participants with a score of 10 or more at baseline, who reach 7 or fewer by week 24.

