### 3.6 Tertiary outcome measures

The tertiary objectives will be measured using the PHQ-9, which is a participant-reported measure of depressive symptomatology. Additionally, the objective will be measured using the Athens Insomnia Scale, which is participant-reported measure of sleep difficulty.

- The outcome measure for **reliable improvement of depressive symptomology** is defined as participants who reach a score reduction of 6 or more from baseline to week 24.
- The outcome measure for **clinically significant improvement of depressive symptomology** is defined as participants with a score of 10 or more at baseline, who reach 9 or fewer by week 24.
- The outcome measure for **recovery of depressive symptomology** is defined as participants with a score of 11 or more at baseline, who reach 8 or fewer by week 24.
- The outcome measure for **reliable improvement of insomnia** has no current, standardised definition, and so in this study, will be defined as participants who reach a score reduction of 50% or more from baseline to week 24.
- The outcome measure for **clinically significant improvement of insomnia** is defined as participants with a score of 6 or more at baseline, who reach 5 or fewer by week 24
- The outcome measure for **recovery of insomnia** is defined as participants with a score of 6 or more at baseline, who reach 4 or fewer by week 24.

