## **6 ELIGIBILITY CRITERIA**

### **6.1 Inclusion criteria**

- Primary working diagnosis of moderate-to-severe GAD indicated via a GAD-7 score of 10 or more at baseline visit
- Previous treatment within an IAPT service with step two low intensity psychological therapy intervention
- Indicated for step three high intensity psychological therapy intervention and on the waiting list OR deemed unsuitable for step two within an IAPT service
- Capable of giving informed consent
- Female participants of child-bearing potential must have a negative urine human chorionic gonadotropin dipstick pregnancy test
- Female participants of child-bearing potential must be practising a highly effective method of contraception (failure rate of less than 1% per year when used consistently and correctly and agree to remain on a highly effective method throughout the 6 or 12 week treatment period. Examples of highly effective contraceptives include: barrier condoms, intrauterine device (IUD), intrauterine hormone-

releasing system (IUS), vasectomised partner, sexual abstinence (refraining from heterosexual intercourse), and oestrogen and progestogen containing hormonal contraception associated with ovulation.

- 18 years of age or above at baseline visit
- Able to understand written and verbal English

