##### GAD-7

*See Appendix A*

The second assessment will be the GAD-7, which is a participant-reported screening tool and severity measure for generalised anxiety disorder (GAD). The GAD-7 score is calculated by assigning scores of 0, 1, 2 and 3, to the responses categories of "not at all", "several days", "more than half the days" and "nearly every day", respectively to 7 problems over the last 2 weeks, and adding together the scores for the 7 problems. The maximum score is 21. Scores of 5, 10 and 15 are taken as the cut-off points for mild, moderate and severe anxiety.

The research nurse will administer the GAD-7 and record the data either directly into the electronic patient record (PCMIS) if available (and therefore the PCMIS record will act as source data), or into a Case Report Form (CRF) if not available (and therefore the CRF will act as source data) and then transpose the data into PCMIS or scan the CRF into the electronic file.

It is anticipated that this assessment will take approximately 5 minutes.

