## **11 STATISTICS AND DATA ANALYSIS**

### **11.1 Sample size calculation**

If Alpha-Stim AID CES has a comparable effect to IAPT high intensity psychological therapy interventions in patients with a primary working diagnosis of GAD, it will achieve an effect size of 1.04 (95% CI 0.88 to 1.23) in an intention to treat sample of 4,183 participants with pre-treatment GAD-7 score of 14.06 (s.d. 5.11) and post treatment GAD-7 score of 8.10 (s.d. 6.37) (Richards and Borglin, 2011). Reliable improvement was obtained after IAPT treatment for generalised anxiety disorder in 54.7%, reliable improvement plus clinically significant change in 40.1% and recovery in 46.0%.

However, to make a meaningful economic impact on NHS care, then Alpha-Stim AID CES does not need to be as effective as IAPT high intensity psychological therapy interventions. In a previous randomised controlled trial (Barclay and Barclay 2014), Alpha Stim CES reduced the mean Hamilton Anxiety score from 29.5 to 13.4 while sham Alpha Stim CES reduced it from 27.6 to 20.0 over 5 weeks  $p=0.001$ ,  $d=0.94$ , with 83% patients showing a drop of 50% in HAM-A score.

A meta-analysis of 14 Alpha Stim CES randomised controlled trials estimates an average effect size of 0.60. On this basis reliable improvement may be seen in 33%, reliable improvement plus clinically significant change in 24% and recovery in 28% cases.

The cost of IAPT high intensity psychological therapy intervention is estimated to be £2,895.00 per participant and £2,914.00 if stepped care was involved (Radhakrishnan et al, 2013). On a cost offset basis if Alpha-Stim AID CES cost £465.00, then reliable improvement plus clinically significant change (which would not necessitate high intensity treatment) in only 20% would be clinically and cost effective.

Taking all data into account, 60 patients would be required to complete Alpha Stim AID CES treatment and all assessments. However, to allow for drop-out from assessments, drop-out from Alpha-Stim AID CES, and choice in relation to IAPT high intensity psychological therapy intervention ,120 patients will be recruited.

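### The GAD-7 categories give an improvement label to falls of 1 to 4 points, below the plan's own 5-point rule, and pool unchanged with worsened participants

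*Combined protocol and SAP*

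**What the plan says.** The primary outcome bullet in section 3.4, repeated in the Study Summary (Primary row), builds a three-level scale from the GAD-7 change between baseline and week 24.

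- Top level, reliable improvement: a fall of at least 5 points, which the protocol regards as clinically important.
- Middle level: "Some reliable improvement is defined as participants who reach a score reduction of 1 – 4 from baseline to week 24".
- Bottom level: "No reliable improvement is defined as participants who reach no score reduction from baseline to week 24".

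Neither place defines a class for a higher score at week 24. For the PHQ-9, section 3.6 uses a single cut: reliable improvement "is defined as participants who reach a score reduction of 6 or more from baseline to week 24". The Athens scale also has a single cut, at 50%. Neither has a middle tier, and neither has a deterioration class.

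The primary objective (section 3.1) names three criteria: reliable improvement, clinically significant improvement and recovery. The middle tier is not among them. Section 11.3 plans means and standard deviations at each visit and does not describe a table of categories.

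**The concern.** If a fall of 5 is what makes a change reliable, a fall of 1 to 4 is not reliable, whether in part or in whole. The plan gives it an improvement label all the same. It follows that a participant who falls by 3 points is not classed as lacking reliable improvement, although the 5-point rule says that is exactly their position. The bullet contradicts itself.

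The bottom class has a separate problem. A participant at 12 on both occasions and one who goes from 12 to 19 receive the same label. The scale leaves room for this: entry is at 10 or more, and section 7.4 states "The maximum score is 21. Scores of 5, 10 and 15 are taken as the cut-off points for mild, moderate and severe anxiety". A rise of 5 is possible from any baseline score of 10 to 16.

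The study describes no comparator arm, so nothing in its own data would show how common a fall of 1 to 4 points is without any effect. The results are meant mainly as evidence for NICE and NHS England. Such readers need to see which changes meet the stated rule and how many participants were worse at week 24.

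**Working it through.** **1. The plan's own figures do not use the middle tier.** Section 11.1 cites a cohort in which "Reliable improvement was obtained after IAPT treatment for generalised anxiety disorder in 54.7%, reliable improvement plus clinically significant change in 40.1% and recovery in 46.0"%. Multiplying by the assumed effect size of 0.60:

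- 0.60 × 54.7% = 32.8%, stated as 33%; 120 × 0.33 = 39.6, stated as 40.
- 0.60 × 40.1% = 24.1%, stated as 24%; 120 × 0.24 = 28.8, stated as 29.
- 0.60 × 46.0% = 27.6%, stated as 28%; 120 × 0.28 = 33.6, stated as 34.

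All three counts are reproduced from the three named criteria alone.

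**2. Which measurement error fits a 5-point rule.** The documents give no reliability for the GAD-7, so it has to be assumed. Section 11.1 gives "pre-treatment GAD-7 score of 14.06 (s.d. 5.11) and post treatment GAD-7 score of 8.10 (s.d. 6.37"). With SD 5.11 and reliability r, the 95% bound for a difference of two scores is 1.96 × 5.11 × √(2(1 − r)).

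| r | SE of difference | 95% bound |
|---|---|---|
| 0.7 | 3.96 | 7.8 |
| 0.8 | 3.23 | 6.3 |
| 0.9 | 2.29 | 4.5 |

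Of these, only r = 0.9 gives a bound that 5 points would just clear. It is used below.

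**3. Hand calculation with no true change.** Treat the change as normal with mean 0 and SD 2.29, with a half-point correction for whole-number scores.

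- Fall of 1 to 4: Φ(4.5/2.29) − Φ(0.5/2.29) = 0.975 − 0.586, about 39%.
- Fall of 5 or more: 1 − 0.975, about 2.5%.

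This ignores entry selection and the 0 to 21 limits.

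**4. Simulation with selection and limits.** Inputs:

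- True score normal with SD 5.11 × √0.9 = 4.85. The mean is 14.06 (section 11.1) or, as an assumption, 12.
- Independent error on each occasion with SD 5.11 × √0.1 = 1.62.
- Scores rounded and limited to 0 to 21.
- A score of 10 or more required at identification (section 7.3) and at baseline (section 6.1: "Primary working diagnosis of moderate-to-severe GAD indicated via a GAD-7 score of 10 or more at baseline visit").
- No true change; 4 million draws per scenario.

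| Week-24 change | Mean 12 | Mean 14.06 |
|---|---|---|
| Fall of 5 or more | 2.5% | 2.2% |
| Fall of 1 to 4 | 39.7% | 37.3% |
| No change | 21.1% | 24.6% |
| Any rise | 36.7% | 35.9% |
| of which 5 or more | 1.6% | 1.6% |

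For 120 participants the middle tier would hold 120 × 0.373 = 45 to 120 × 0.397 = 48 people. The bottom class would hold 21.1 + 36.7 = 57.8% or 24.6 + 35.9 = 60.5% of participants. The share of that class with a higher score would be 36.7/57.8 = 63% or 35.9/60.5 = 59%.

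**5. At the plan's own 33% response rate.** Take the change SD as √(5.11² + 6.37² − 2ρ × 5.11 × 6.37), with an assumed correlation ρ of 0.3 to 0.7. This gives 6.87 to 4.60. Set the mean so that 33% fall by 5 or more: 4.5 − 0.44 × SD, or 1.48 to 2.48. The 1-to-4 tier then holds about 23% (SD 6.87) to 34% (SD 4.60). The score limits are not modelled here.

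**The case against.** The strongest reply is that the tier is subsidiary. The primary objective and the planning counts use the 5-point rule, clinically significant improvement and recovery. Section 11.1 itself treats participants with some symptom improvement as people who might reach reliable improvement after a repeat course, so it places them short of it. This stands. A reader might infer that the responder rate is inflated; it is not.

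A reader might also infer that the study will report chance variation as benefit in a headline table. The documents do not say so. Section 11.3 plans only means and standard deviations by visit, and nothing states that the 1-to-4 tier will be added to the responders.

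Nor is deterioration lost. The GAD-7 is collected at all six visits (section 7.6) and copied to the study database (section 12.2), so a count can be made from existing data. Visit means would also reflect worsening in aggregate. What is missing is a prespecified class.

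It would be wrong to describe a rise at week 24 as worsening on the device. Use ends at week 6 or at latest week 12 (section 4), which is 12 to 18 weeks before that assessment, and high intensity therapy may have started in between.

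Lower assumed reliabilities give larger figures. At 0.7 the same simulation reaches about 14% falling by 5 or more, 49% with any fall and 8% rising by 5 or more. Those figures do not sit with a 5-point reliable-change rule, because the 95% bound there is 7.8 points. The documents justify 5 points as clinically important and do not derive it from measurement error, so even the match at 0.9 is an assumption.

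Finally, zero true change is an extreme case. At a 33% response rate some of the 1-to-4 falls would be real. The label would still contradict the rule.

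**Conclusion.** The point holds as an inconsistency of definition. The same bullet sets a 5-point rule, gives an improvement label to changes below it, and defines a bottom class that cannot separate unchanged from worse. This rests on the text alone and needs no assumption.

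Its practical size does rest on assumptions. With no true change, reliability 0.9, SD 5.11 and entry at 10 or more, about 37–40% would carry the middle label, against about 2% who meet the 5-point rule. About 36–37% would score higher, roughly 1.6% by 5 or more, and all of these would be pooled with the unchanged. If the two upper tiers were ever added together, some 39–42% would appear improved with no effect.

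This should be corrected, but it does not threaten the main criteria: the 5-point responder rate, clinically significant improvement, recovery and the counts of 40, 29 and 34 are unaffected.

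**What to change.** In section 3.4 and in the Primary row of the Study Summary, classify the GAD-7 change from baseline to week 24 as:

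- reliable improvement: a fall of 5 or more;
- no reliable change: within 4 points either way;
- reliable deterioration: a rise of 5 or more.

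Delete the middle label. State in section 11.3 that counts will be reported for all three classes, and show small falls only in the distribution of change scores. Note beside the table that a baseline score of 17 or more leaves no room for a 5-point rise (21 − 17 = 4), so the deterioration count is limited for those participants.

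The cost is wording and one extra table row, with no new data, visits or participants. The presentation becomes slightly less favourable if the 1-to-4 tier would otherwise have been shown as improvement.

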It is anticipated from a sample size of 120, then at least 40 (33%) would show reliable improvement, 29 (24%) plus clinically significant improvement, and 34 (28%) recovery at 6 months. Since a repeat course of Alpha-Stim from 6 to 12 weeks can result in further improvement in those who have made some improvement in symptoms, we estimate that a further 20 (17%) will make a reliable improvement in their symptoms. Therefore, it is anticipated that 60 (50%) will make a reliable improvement in their GAD-7 symptoms requiring no additional psychological treatment or a minimal psychological treatment intervention (in those with other symptoms or do not make a reliable improvement plus clinically significant change).

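### The 24% forecast and 20% cost-offset figure in section 11.1 are for a composite that section 3.4 does not list; the 3.4 outcome with nearly the same name needs no minimum fall and is easier to meet

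*Combined protocol and SAP*

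**What the plan says.** Section 3.4 and the Study Summary list three primary GAD-7 outcomes.

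- Reliable improvement needs a fall of at least 5 points by week 24, which the plan regards as clinically important. The next grade down is: "Some reliable improvement is defined as participants who reach a score reduction of 1 – 4 from baseline to week 24".
- Clinically significant improvement is met by "participants with a score of 10 or more at baseline, who reach 9 or fewer by week 24".
- Recovery is met by "participants with a score of 10 or more at baseline, who reach 7 or fewer by week 24".

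Section 6.1 admits patients with moderate-to-severe GAD "indicated via a GAD-7 score of 10 or more at baseline visit".

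Section 11.1 works with a fourth quantity. Its cost-offset argument is that "reliable improvement plus clinically significant change (which would not necessitate high intensity treatment) in only 20% would be clinically and cost effective". The same composite carries the 40.1% benchmark from routine high intensity therapy and the 24% forecast for the device. When section 11.1 turns the forecasts into counts, it writes "29 (24%) plus clinically significant improvement, and 34 (28%) recovery at 6 months".

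Section 11.3 plans means and standard deviations by visit. It describes no responder analysis.

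**The concern.** The entry floor and the responder cut-off meet: 10 gets a patient in, and 9 makes that patient a clinically significant improver. Someone who moves one point is placed by the plan's own grading below reliable improvement, yet meets another primary outcome. The study has a single treated group and no control, so crossings due to measurement variation or regression to the mean cannot be subtracted.

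The sharper problem is the mismatch of names. Section 11.1 argues from a composite that requires both a 5-point fall and a score of 9 or fewer. Section 3.4 will produce a rate that requires only the second condition. The wording of the counts in 11.1 attaches the 24% to the term that 3.4 uses for the looser outcome. A reader of the final report, which is intended for NICE and NHS England, could set the wrong rate beside 24% or 20%. Publishing the reliable-improvement rate separately does not prevent this, because two marginal rates do not give the joint rate.

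**Working it through.** **1. Reproduce the plan's forecasts.** Inputs from section 11.1: benchmark rates of 54.7% (reliable improvement), 40.1% (composite) and 46.0% (recovery), effect size 0.60, n = 120. Multiplying each rate by 0.60:

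- reliable improvement: 0.60 × 54.7 = 32.8, stated as 33%; 120 × 0.33 = 39.6, stated as 40
- composite: 0.60 × 40.1 = 24.06, stated as 24%; 120 × 0.24 = 28.8, stated as 29
- recovery: 0.60 × 46.0 = 27.6, stated as 28%; 120 × 0.28 = 33.6, stated as 34

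All three reproduce, so the 24% is a forecast of the composite.

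**2. Enumerate the scores.** Baseline-to-week-24 pairs that meet clinically significant improvement with a fall below 5: 10 to 9, 8, 7 or 6; 11 to 9, 8 or 7; 12 to 9 or 8; 13 to 9. That is ten pairs, the smallest fall being 1 point. For recovery there are three: 10 to 7, 10 to 6 and 11 to 7, the smallest fall being 3 points.

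**3. A bound that needs no distribution.** Under 3.4, everyone at 7 or fewer is also at 9 or fewer, so the clinically significant improvement rate cannot be below the recovery rate. If recovery is 28%, the 3.4 improvement rate is at least 28% and cannot be the 24%. The plan's own forecasts therefore imply a gap of at least 28 − 24 = 4 points (34 − 29 = 5 of 120).

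**4. Illustrative size at the plan's effect.** Taken from 11.1: baseline mean 14.06, s.d. 5.11; mean fall 0.60 × 5.11 = 3.07. Assumed: normal scores, rounded and limited to 0–21, baseline kept at 10 or more; week-24 s.d. either 6.37 (the benchmark's post-treatment value) or 5.11; correlation 0.3 to 0.7.

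| Week-24 s.d. | Correlation | 3.4 improvement % | Composite % | Gap, points |
|---|---|---|---|---|
| 6.37 | 0.3 | 36.8 | 31.8 | 4.9 |
| 6.37 | 0.5 | 33.8 | 28.3 | 5.5 |
| 6.37 | 0.7 | 30.9 | 24.1 | 6.7 |
| 5.11 | 0.3 | 34.6 | 28.7 | 5.8 |
| 5.11 | 0.5 | 31.6 | 25.0 | 6.6 |
| 5.11 | 0.7 | 28.6 | 20.4 | 8.2 |

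Gaps are taken before rounding. Of 120, they are about 6 (120 × 0.049 = 5.9) to 10 (120 × 0.082 = 9.8) participants.

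**5. Sensitivity.** A second assumed model takes the same baseline kept at 10–21 (about 36% then enter at 10–13, where a fall of 4 or less can be enough) and adds a normal change with a given mean and s.d.

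| Mean fall | s.d. of change | 3.4 % | Composite % | Gap, points |
|---|---|---|---|---|
| 0 | 2.0 | 6.7 | 0.6 | 6.1 |
| 0 | 4.0 | 14.3 | 8.0 | 6.3 |
| 0 | 6.9 | 23.7 | 19.1 | 4.5 |
| 2 | 2.0 | 19.1 | 5.5 | 13.6 |
| 2 | 4.0 | 25.3 | 17.3 | 8.0 |
| 2 | 4.6 | 27.1 | 19.9 | 7.2 |
| 2 | 6.9 | 32.5 | 27.6 | 4.9 |
| 3.07 | 2.0 | 28.2 | 12.8 | 15.4 |
| 3.07 | 6.9 | 37.7 | 32.8 | 5.0 |

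The gap runs from 4.5 to 15.4 points and is widest when the spread of change is small. With s.d.s of 5.11 and 6.37, the s.d. of change is √(5.11² + 6.37² − 2 × r × 5.11 × 6.37). This is 6.9 at r = 0.3 and 4.6 at r = 0.7; a value of 2.0 would need r of about 0.96. The middle and lower gaps therefore fit the cited figures better.

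**6. Margin.** 24 − 20 = 4 points. Every gap in steps 4 and 5 is larger.

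**The case against.** The strongest reply is that the plan never makes the substitution. Section 11.1 attaches 20% to the composite by name, and the composite can be assembled from two outcomes that 3.4 does define. Reporting change and threshold crossing separately is a legitimate choice, and section 3.1 ties the terms to NHS IAPT definitions. All of this stands. It is why the existing definitions should stay, but it does not supply the missing outcome or its analysis.

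A reader might go further and infer four things that the documents do not support.

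- That the study could be declared a success on a 1-point fall. There is no formal success rule; the 20% is a cost-offset remark within the sample size section. A fall from 10 to 9 would also not count as reliable improvement.
- That the composite would miss 20% while the 3.4 rate reaches it. This depends on the assumptions. At a 2-point fall with an s.d. of change of 2.0, even the 3.4 rate is 19.1%. At the same fall the composite reaches about 20% once the s.d. is about 4.6, and at the plan's effect size it is 20.4% to 31.8% in step 4.
- That the 28% forecast is also orphaned. Recovery is defined in 3.4, so it is not.
- That clinically significant improvement itself should be redefined to need a 5-point fall. A participant entering at 10 would then have to reach 5, and one entering at 11 would have to reach 6, which is stricter than recovery at 7 or fewer.

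**Conclusion.** The point holds as a mismatch between the listed outcomes and the figures against which they will be read. It is certain from the text that the 3.4 threshold outcomes carry no minimum fall, that 40.1%, 24% and 20% belong to the composite, and that neither 3.4, the Study Summary nor 11.3 provides for that composite. The plan's own forecasts put the 3.4 rate at least 4 points above it.

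The further size is illustrative. It is 4.9 to 8.2 points at the 0.60 effect with correlations of 0.3 to 0.7, and roughly 5 to 15 points over wider assumptions. The documents give neither a baseline-to-week-24 correlation nor a score distribution for patients entering at 10 or more, so these figures rest on the cited benchmark mean and s.d. and on assumed normality.

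**What to change.** Keep the three existing GAD-7 definitions. In section 3.4 and the Study Summary, add a composite outcome: baseline 10 or more, week-24 score of 9 or fewer, and a fall of 5 or more. In section 11.1, state that 40.1%, 24% and 20% refer only to this composite, and reword the sentence giving the counts so that the 29 is named as the composite. In section 11.3, report the composite proportion with a confidence interval, and report recovery with and without the 5-point fall. The interval matters: at 24% of 120 its half-width is 1.96 × √(0.24 × 0.76 / 120) = 7.6 points, wider than the margin over 20%.

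The same structure appears in section 3.6. On the PHQ-9 a fall from 10 to 9 qualifies against a 6-point rule, and a matching composite may be added. The Athens outcome, "participants with a score of 6 or more at baseline, who reach 5 or fewer by week 24", has the same form, but no change is required there: adding the plan's 50% rule would make it as strict as or stricter than Athens recovery for participants entering at 6 to 9.

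The cost is wording and one extra tabulation from scores already collected. The rate set against 20% and 24% will be less favourable. The change should be made before results are seen.
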